APPENDIX A: STUDY FORMS

APPENDIX B: CERTIFICATION FORMS

APPENDIX C: QUALITY OF LIFE QUESTIONNAIRES

APPENDIX D: PATIENT CALENDARS

APPENDIX E: UPRC MANUAL

APPENDIX F: TABLE FOR ASSESSING UVEITIS ACTIVITY

Investigators, Personnel and Study Sites

[REDACTED]

[REDACTED]
[REDACTED]
[REDACTED]

[REDACTED]

[REDACTED]

[REDACTED]

[REDACTED]

[REDACTED]

[REDACTED]
[REDACTED]

[REDACTED]

[REDACTED]

[REDACTED]

[REDACTED]

[REDACTED]

[REDACTED]
[REDACTED]

[REDACTED]

[REDACTED]

[REDACTED]

[REDACTED]

[REDACTED]

[REDACTED]
[REDACTED]

[REDACTED]

[REDACTED]

[REDACTED]

[REDACTED]
[REDACTED]

[REDACTED]

[REDACTED]
[REDACTED]

[REDACTED]

[REDACTED]
[REDACTED]

[REDACTED]

[REDACTED]

[REDACTED]

[REDACTED]

[REDACTED]

[REDACTED]

[REDACTED]

[REDACTED]
[REDACTED]

[REDACTED]

[REDACTED]
[REDACTED]

[REDACTED]

[REDACTED]
[REDACTED]

Data Safety and Monitoring Committee (DSMC) Members

[REDACTED]

[REDACTED]

[REDACTED]

[REDACTED]

[REDACTED]

[REDACTED]

[REDACTED]

[REDACTED]

[REDACTED]

[REDACTED]

[REDACTED]

[REDACTED]

[REDACTED]

[REDACTED]

[REDACTED]

Background

In the First-line Antimetabolites as Steroid-sparing Treatment (FAST) Uveitis Trial, we propose to establish which immunosuppressive therapy, methotrexate or mycophenolate mofetil, is more effective as a first-line, corticosteroid-sparing agent for the treatment of non-infectious uveitis. Uveitis, a set of conditions defined by intraocular inflammation, is a significant cause of vision loss and morbidity in the United States and the world.^{1, 2} The incidence was recently estimated to be more than 50 cases per 100,000 person-years, with a prevalence of approximately 115 per 100,000 persons.³ Additionally, uveitis is believed to be the cause of up to 10% of cases of legal blindness in the United States, or approximately 30,000 new cases of blindness per year.^{1, 3, 4} In contrast to common age-related eye disorders, uveitis may have a stronger socio-economic impact because it disproportionately affects younger working-age patients.⁵ Although the etiology of uveitis is varied, most cases are presumed to be immune-mediated and lack a known infectious cause.⁶⁻⁹ Even in developing countries such as India that have a larger burden of infection, the vast majority of cases are non-infectious.^{10, 11}

The current mainstay of treatment for non-infectious uveitis is corticosteroids (topical, systemic, locally injected, or corticosteroid-eluting implants). Due to the well documented local and systemic side effects associated with corticosteroid therapy, other immunosuppressive therapies are frequently used as corticosteroid-sparing agents in patients who need long-term therapy. These include antimetabolites, calcineurin inhibitors, alkylating agents, and biologic drugs.¹² Cost and morbidity associated with uncontrolled inflammation make the selection of an effective initial steroid-sparing agent extremely important.

When corticosteroid-sparing therapy is required, the two most commonly used first-line immunosuppressive agents are methotrexate and mycophenolate mofetil.¹³ Because of cost and potentially dangerous long-term side effects, other classes of drugs such as biologics are typically reserved for refractory cases in which other treatments have failed.¹² It is common practice for patients requiring a steroid-sparing agent to be treated first with the less expensive methotrexate and then switched to mycophenolate mofetil in the event of treatment failure. However, results from non-comparative retrospective case series indicate that uveitis patients may be much more likely to achieve controlled inflammation and tolerate treatment with mycophenolate mofetil.¹³⁻²⁸ Furthermore, approximately half of the patients who fail treatment with methotrexate go on to successful treatment with mycophenolate mofetil.²⁹ Unlike in rheumatology, where clinical trials have demonstrated differential efficacy of antimetabolites for systemic inflammatory diseases, there have been no prospective randomized, controlled trials in uveitis to systematically determine which antimetabolite is more clinically efficacious as initial corticosteroid-sparing therapy. This makes it difficult for clinicians to make informed, evidence-based decisions about first-line immunosuppressive treatment. In addition, if patients fail one antimetabolite, there is no evidence basis for deciding whether to switch to another antimetabolite, or to move on to another class of immunosuppressives, including biologics.

1. Introduction to trial

The proposed study is a randomized comparative effectiveness trial to determine which treatment, methotrexate or mycophenolate mofetil, is more effective as first-line corticosteroid-sparing treatment for patients with non-infectious intermediate, posterior and panuveitis requiring corticosteroid-sparing therapy.

Two hundred sixteen patients with non-infectious uveitis in need of corticosteroid-sparing therapy will be randomized to receive either oral methotrexate or oral mycophenolate mofetil at

They will be followed monthly for 6 months after enrollment or until treatment failure. Patients who achieve success at 6 months will continue for another 6 months on the same medication. Patients who fail at 6 months will switch treatments and be followed for an additional 6 months or until failure of the second treatment.

1.1. Research question

Which treatment—methotrexate or mycophenolate mofetil—is more effective as a first-line immunosuppressive treatment for patients with non-infectious intermediate, posterior and panuveitis requiring corticosteroid-sparing therapy?

1.2. Specific aims

Aim 1: Establish which immunosuppressive treatment, methotrexate or mycophenolate mofetil, results in a higher proportion of patients achieving corticosteroid-sparing control of inflammation. As a primary outcome, proportion of successful corticosteroid-sparing control of inflammation will be compared at 6 months after enrollment. We will also evaluate differences in secondary outcomes, such as visual acuity, macular thickness, time to control of inflammation, efficacy within various anatomic locations of uveitis, tolerability, quality of life, and adverse events.

Aim 2: Evaluate the clinical efficacy of switching agents after initial treatment failure. Patients who are recorded as a treatment failure on the initial randomized drug will be switched to the other treatment. These patients will be followed an additional 6 months from the date of treatment failure, following the same protocol with the same primary and secondary outcomes as in Aim 1.

2. Trial design

2.1. Design summary

Study type

- Randomized, observer-masked comparative effectiveness trial
- Block randomization by site: [REDACTED]
- Sample size: 216 patients, 108 patients per arm (Table 1)

Treatment arms

- Oral methotrexate
- Oral mycophenolate mofetil

Treatment timeline

- Phase I
 - Initial treatment from 0-6 months. If treatment success (i.e. achieving corticosteroid-sparing control of inflammation at 6 months), treatment extended to 12 months.
- Phase II
 - Second therapy initiated after failure to achieve corticosteroid-sparing control of inflammation in Phase I (0-6 months).

Outcomes

- **Primary outcome (Specific Aim 1):**
 - Proportion of overall treatment success at 6 months, where treatment success is defined as controlled ocular inflammation (Table 2) with 7.5 mg/day of oral prednisone and ≤ 2 drops/day of topical 1% prednisolone acetate
- **Secondary outcomes**
 - Proportion of corticosteroid-sparing treatment success at 6 months after switching treatments in patients who are a treatment failure in the first 6 months where treatment success is defined as in Aim 1 (**Specific Aim 2**)
 - Time to control of inflammation
 - Time to treatment success
 - Proportion achieving treatment success at 5 months and sustaining, for at least 28 days, to 6 months
 - Proportion achieving treatment success at 12 months in Phase I
 - Phase I treatment success (6-12 months) with complete discontinuation of corticosteroid
 - Proportion achieving treatment success at 6 months in Phase II
 - Change in best spectacle-corrected visual acuity (BSCVA)
 - Presence of macular edema
 - Change in macular thickness
 - Change in vitreous haze as assessed clinically by the Miami (formerly Davis) scale
 - Change in vitreous haze as assessed by fundus photography grading by NEI and Miami (formerly Davis) scales
 - Efficacy for intermediate, posterior and panuveitis subgroups
 - Efficacy for retinal vasculitis
 - Proportion discontinuing due to intolerability
 - Rate of adverse events
 - Proportion discontinuing due to serious adverse events
 - Quality of life (Health related and vision related)

- Dose reduction
- Efficacy of treatment in patients with Vogt-Koyanagi-Harada (VKH) disease
- Proportion of patients beginning with at least 2+ inflammation in anterior chamber cells who experience a 2-step reduction (i.e. decreasing from 2+ to 0.5+; 3+ to 1+; 4+ to 2+).
- Proportion of patients beginning with at least 2+ inflammation in vitreous haze who experience a 2-step reduction (i.e. decreasing from 2+ to 0.5+; 3+ to 1+; 4+ to 2+).
- Proportion of patients who started with at least 1+ inflammation levels in anterior chamber cells who achieve a decrease to 0 level of inflammation in anterior chamber cells.
- Proportion of patients who started with at least 1+ inflammation levels in vitreous haze who achieve a decrease to 0 level of inflammation in vitreous haze.
- Proportion of patients achieving controlled inflammation defined by 0 level of inflammation in vitreous haze and 0 level of inflammation in anterior chamber cells
- Proportion of patients requiring injections for severe inflammation during the trial
- Proportion of patients requiring injections for macular edema during the trial

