2.3.2. Inclusion Criteria

All the following criteria must be met at enrollment:

- History of non-infectious intermediate, anterior and intermediate, posterior or panuveitis in at least one eye
- Active inflammation within the last 180 days, defined by the presence of **any of the following** (in at least one eye) according to SUN criteria and the NEI vitreous haze grading scale:
 - ≥ 2+ anterior chamber cells and/or
 - ≥ 2+ vitreous haze and/or
 - active retinal or choroidal inflammation
- Active inflammation in at least one eye at enrollment, defined by **any of the following**:
 - ≥ 1+ anterior chamber cells and/or
 - ≥ 1+ vitreous haze and/or
 - active retinal/choroidal inflammation (bullous serous retinal detachment qualifies if choroidal thickening)
- **At least one** of the following criteria must be met before or at enrollment:
 - 1.) Active inflammation after 4 weeks of high-dose (1mg/kg prednisone equivalent) oral corticosteroid treatment
 - 2.) Treatment with oral corticosteroids resulting in a reduction of inflammation, followed by an increase in inflammation (of at least 1 grade in anterior chamber cells or vitreous haze or a change of non-active to active retinal/choroidal lesions) when corticosteroid is tapered, in the 180 days prior to enrollment
 - 3.) Treatment with ≥10mg/day oral prednisone or equivalent over at least the past 90 days prior to enrollment
 - 4.) Active inflammation after long-acting corticosteroid injection 4 weeks to 180 days prior to enrollment
 - 5.) One of the following uveitic conditions necessitating corticosteroid-sparing immunosuppressive treatment¹²:
 - Behcet's disease with posterior segment involvement
 - Multifocal choroiditis with panuveitis
 - Serpiginous choroidopathy
 - Birdshot retinochoroidopathy
 - Diffuse retinal vasculitis
 - Severe Vogt-Koyanagi-Harada syndrome (VKH) (for example: acute VKH that has been active for at least 4 weeks, or VKH with bullous serous retinal detachments and/or choroidal detachments with other signs of ocular inflammation)
 - Sympathetic ophthalmia
 - 6.) If the patient does not fit any of these categories, but the physician believes corticosteroid-sparing immunosuppressive therapy is indicated, eligibility may be assessed on a case-by-case basis after discussion with the coordinating center. Please contact [REDACTED] or by email.

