2.5. Definitions for primary endpoint

2.5.1. Determination of Treatment Success/Failure

Treatment success is defined as controlled ocular inflammation (see Table 2) in both eyes with 7.5 mg/day of prednisone, no periocular or intravitreal corticosteroid injections after the first 90 days of follow up, and ≤ 2 drops/day of topical 1% prednisolone acetate at the 6 month visit without treatment failure any point due to safety, tolerability or futility. Patients can stop medication at any time, but that in and of itself does not count as a treatment failure.

Table 2: Criteria for controlled inflammation

Parameter	Definition of control
Anterior chamber cells*	$\leq 0.5+$
Vitreous haze**	$\leq 0.5+$
Choroid & retina***	No active inflammation or retinal vasculitis posterior to the equator

*SUN criteria³⁰; ** NEI vitreous haze grading scale³¹ *** Cystoid macular edema is not sufficient to be called active inflammation

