2.5.4 Primary Endpoint Flowchart

*Criteria for controlled inflammation: Anterior chamber cells ≤ 0.5 +; Vitreous haze ≤ 0.5 +; No active choroid and retina lesions

** 2 drops/day refers to topical 1% prednisolone acetate or equivalent

3. Treatment plan

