Assessment and follow-up depends on the status of the eye. Eyes classified as type E above are recorded as such at baseline, and never provide eye outcome related data. Because (a) inability to assess parts of the eye could be related to the progression of disease, but (b) inability to assess in the absence of signs of disease cannot be considered evidence of treatment failure, we use the following table to summarize how success at six months will be scored. In this table, the row corresponds to the status of an eye at baseline, and the column to the status of the eye considering the primary outcome of success at six months.

	Month 6: A	Month 6: B	Month 6: C	Month 6: D	Month 6: E
Baseline: A	Success	See below**	Fail	Fail	Fail*
Baseline: B	Success	See below**	Fail	Fail	Fail*
Baseline: C	Success	See below**	Fail	Fail	Fail*
Baseline: D	Success	See below**	Fail	Fail	Fail*
Baseline: E	NA	NA	NA	NA	NA

Specifically, note that an eye which is fully assessable at six months and which does not meet the specific criteria for failure of control is always considered a success. Eyes which are fully or partially assessable and which meet any of the criteria for failure are always considered to have failed. However, eyes which are only partially assessable but which meet no criteria in the assessable region may be scored successes or failures depending on their baseline status (see next paragraphs below). Eyes which were present at baseline but which are missing at the end of the study are listed as Fail* in the table; we propose to consider such eyes to have failed unless a specific reason demonstrates that the loss of the eye was completely unrelated to the presence or progression of disease.

The primary analysis is at the patient level. Both eyes must meet the success criteria for the patient to be considered a success.

****Incompletely assessable eyes.** Uveitis assessment for this purpose is based on (i) assessment of anterior cells, (ii) vitreous haze, and (iii) retinal or choroidal lesions. In the pilot study, (iv) assessment of vitreous cells was also used. We will have longitudinal measurements of inflammation according to the following schedule: anterior chamber cells, vitreous haze and

active retinal/choroidal lesions will be measured at Baseline, Week 2, Month 1 and every subsequent 4 weeks until the 6 month assessment (Phase I or Phase II) or 9 and 12 month assessment (Phase I 6-12 months).

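### One secondary outcome labelled controlled inflammation omits the retina and choroid, so a patient with an active posterior lesion and exactly 0 cells and 0 haze meets it, even at baseline

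*Combined protocol and SAP*

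**What the plan says.** The outcome is one of the secondary outcomes in protocol section 2.1: "Proportion of patients achieving controlled inflammation defined by 0 level of inflammation in vitreous haze and 0 level of inflammation in anterior chamber cells". It gives no time point, no rule for combining the two eyes and no baseline restriction. The two outcomes immediately before it do have a restriction. The haze version, for example, begins "Proportion of patients who started with at least 1+ inflammation levels in vitreous haze".

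The documents define control with three components elsewhere:

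- **Protocol section 2.5.1, Table 2** (the criteria for controlled inflammation) requires anterior chamber cells ≤0.5+, vitreous haze ≤0.5+ and, for choroid and retina, "No active inflammation or retinal vasculitis posterior to the equator".
- **Protocol section 2.5.4**, the primary endpoint flowchart, repeats the three, ending with "No active choroid and retina lesions".
- **SAP section 3.1** states: "Uveitis assessment for this purpose is based on (i) assessment of anterior cells, (ii) vitreous haze, and (iii) retinal or choroidal lesions".

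On entry, protocol section 2.3.2 has a criterion headed "Active inflammation in at least one eye at enrollment, defined by", under which any one of three findings is enough. The third is "active retinal/choroidal inflammation (bullous serous retinal detachment qualifies if choroidal thickening". The separate 180-day activity criterion has the same structure, and its third alternative is "active retinal or choroidal inflammation".

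The SAP does not define the combined outcome. Its secondary objectives in section 2.3.1 include the two separate reductions to 0, one for cells and one for haze, but not the combination. Nor does the combination appear among the variables in SAP section 3.2.1 or the planned secondary analyses in section 3.2.2.

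**The concern.** The outcome takes a term that the protocol has defined and gives it a different meaning: stricter on two components and silent on the third. Posterior uveitis, whose primary site is the retina or choroid (protocol section 2.3.1), is part of the target population, and posterior activity alone is enough for entry. A patient can therefore enter with nothing in the anterior chamber or vitreous and an active lesion behind. Under this outcome that patient has achieved control before the first dose.

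Two things are at stake. First, the report could count active posterior disease as control, and the same patient could be a success on this outcome and a failure on the primary endpoint at the same visit. Second, patients who qualify regardless of treatment stay in the denominator. They raise both arms' rates and pull the observed difference towards zero.

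**Working it through.** **Step 1. Compare the definitions.** Take three patients with the findings below; the grades hold in both eyes.

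| Findings | Secondary outcome (2.1) | Table 2 (2.5.1) |
|---|---|---|
| Cells 0, haze 0, active choroidal lesion | Met | Not met |
| Cells 0.5+, haze 0, retina and choroid quiet | Not met | Met |
| Cells 0.5+, haze 0, active choroidal lesion | Not met | Not met |

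Rows 1 and 2 show that neither definition contains the other. Row 1 is the fault. At baseline, that patient satisfies the enrollment activity criterion in section 2.3.2 through its third alternative. Row 3 marks the limit: a grade of 0.5+ in either field is not level 0, so that patient is not misclassified.

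**Step 2. Look for a planned figure.** The documents give no rate, sample size or power for this outcome, so there is nothing to reproduce for it. Any numerical illustration has to borrow the primary planning inputs from SAP section 3.4.1: 40% versus 60%, two-sided alpha 0.05, 80% power and 10% loss. These reproduce the trial size:

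- The two-proportion formula with pooled variance under the null gives 97 per arm. 97/0.9 = 107.8, so 108 per arm and 216 in total, as stated.
- SAP equation (5) gives 2N = 4 × (1.960 + 0.842)² × 0.25 / 0.20² = 196.2. 196.2/0.9 = 218, within 1% of 216.

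**Step 3. Dilution.** Let f be the share of each arm that is 0/0 at baseline and stays 0/0 on either drug. Let p be the rate among the others. Then

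- observed rate = f + (1−f)·p
- observed difference = (1−f)·(p₁ − p₀)

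**Step 4. Illustration.** The documents do not give f; 5 to 40% is an assumed range. With n = 97 evaluable per arm and p₀ = 0.40, p₁ = 0.60 among the others, let a and b be the observed arm rates and m their mean. Power is

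Φ{ [ (b−a)√n − 1.96√(2m(1−m)) ] / √( a(1−a) + b(1−b) ) }.

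For f = 10%: a = 0.46, b = 0.64, m = 0.55. This gives (0.18 × 9.849 − 1.96 × 0.7036)/0.6920 = 0.569, and Φ(0.569) = 0.715.

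The last two columns show the same calculation when the 0/0 patients are left out of the denominator, as the second repair below would do.

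| f | Arm rates | Difference (points) | Power, all included | n per arm if restricted | Power if restricted |
|---|---|---|---|---|---|
| 0 | 0.40 / 0.60 | 20 | 0.800 | 97 | 0.800 |
| 5% | 0.43 / 0.62 | 19 | 0.759 | 92 | 0.779 |
| 10% | 0.46 / 0.64 | 18 | 0.715 | 87 | 0.756 |
| 20% | 0.52 / 0.68 | 16 | 0.625 | 77 | 0.703 |
| 30% | 0.58 / 0.72 | 14 | 0.534 | 67 | 0.642 |
| 40% | 0.64 / 0.76 | 12 | 0.445 | 58 | 0.579 |

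Under these assumptions, leaving the 0/0 patients in costs more power than removing them.

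**The case against.** The best defence is that the outcome says exactly what it counts. It sits among other outcomes on cells and haze and can be read as a stricter companion to Table 2, with 0 in place of ≤0.5+. Control on all three components is already measured by the primary outcome and by the other outcomes built on treatment success. A component outcome may legitimately disagree with a composite one.

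This defence has some force, and it keeps the point small. It does not remove it. A stricter form of Table 2 would keep the retina and choroid row. SAP section 3.1 treats lesions as a binary assessment with its own threshold, so no active lesion is the natural zero level. Protocol section 5.3.2 says which findings fall outside the criteria for controlled inflammation, namely anterior chamber flare and vitreous cells; retinal and choroidal disease is not among them. If only cells and haze were meant, the label is wrong and the baseline restriction used by the neighbouring outcomes is missing.

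A reader might infer more than the documents support:

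- **That every patient with active posterior disease counts as controlled throughout.** This holds only at visits where both grades are exactly 0.
- **That all the posterior conditions named in section 2.3.2 illustrate the problem.** Multifocal choroiditis is listed there in its form with panuveitis, which by the definition in section 2.3.1 also involves the anterior chamber and vitreous. It is a poor example of a 0/0 patient.
- **That the prespecified posterior/panuveitis subgroup analysis is distorted.** That analysis (SAP section 3.2.2) tests treatment success, which uses Table 2 in full.
- **That the trial loses a known amount of power.** The SAP plans no test of this outcome. The 40% and 60% rates belong to the primary endpoint, and f is assumed.

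**Conclusion.** The point holds as a definitional fault in one secondary outcome. The stated rule classes a 0/0 patient with an active retinal or choroidal lesion as controlled, at baseline and at any later visit with both grades 0, where Table 2 classes the same patient as uncontrolled. This follows from the text and needs no assumption about numbers.

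The direction of the effect is clear: higher rates in both arms and a difference multiplied by (1−f). Its size cannot be fixed from the documents. The illustrative range is 19 down to 12 points from a true 20 as f runs from 5 to 40%. It assumes that f is the same in both arms, that these patients stay 0/0 on either drug, and that the primary planning rates apply to the rest.

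The primary endpoint, its anatomic subgroup analysis and the sample size are unaffected. The outcome should be corrected before it is reported, but it does not threaten the trial's main conclusion.

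**What to change.** **Preferred.** Redefine the outcome as 0 anterior chamber cells, 0 vitreous haze and the third row of Table 2 (no active retinal or choroidal inflammation and no retinal vasculitis posterior to the equator), in both eyes, at 6 months. Add it in that form to SAP section 2.3.1, which now omits it.

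**Acceptable alternative.** Keep the two components, rename the outcome as absence of anterior chamber cells and vitreous haze, and restrict it to patients with cells or haze above 0 at baseline. State the eye rule and the time point, and add it to the SAP.

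**Cost.** Either is a change of wording. Retinal and choroidal status is already assessed for the primary endpoint, so no new data are needed. The first option will give lower reported rates; the second a smaller denominator.
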